If a patient was prematurely withdrawn from the study prior to Week 72, all assessments scheduled for Visit 11 were to be performed at the time the patient withdrew. If a patient participating in the optional extension study withdrew prior to commercial drug availability, all assessments scheduled for the optional extension period EOT visit were to be performed.

If a liver biopsy was performed according to the local regulations or standard of care at any time during A4250-008, the biopsy results should have been recorded in the electronic case report form (eCRF). If liver biopsy results were collected for a patient in Study A4250-005 or prior to Week 24 in Study A4250-008, the patient was to be asked to consent to a follow-up liver biopsy at Visit 11, if allowed per local regulations, unless 2 prior liver biopsy results had been collected (with at least 1 year between biopsies). Liver biopsies were not performed in Spain.

For patients not participating in the optional extension period, Visit 12 was to take place 28 days after Visit 11. All patients who were prematurely withdrawn were to have this visit 28 days after the last dose of study drug for AE monitoring and other safety follow-up assessments.

If a patient discontinued before Week 72, additional telephone contacts were to be made every 3 months after the Follow-up visit (Visit 12) up to Week 72 to inquire whether the patient had undergone biliary diversion or liver transplantation, and if ongoing TEAEs at the time of discontinuation had resolved. The telephone calls were to take place up until 72 weeks even if the patient had biliary diversion or liver transplant.

Patients and/or caregivers were instructed to complete the electronic diary (eDiary) every morning and evening for the first 24 weeks (Visits 1 to 5) and for the 21 days before each clinic visit thereafter (Visits 6 to 12). In addition, Cohort 2 patients and/or caregivers were instructed to complete the eDiary during the Screening period. Patients participating in the optional extension period were not to complete eDiary entries after Visit 11. The eDiary included patient-reported outcome (PRO) and observer reported outcome (ObsRO) items for evaluation of itching (using PRO), scratching (using ObsRO), and

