4.2 Secondary Efficacy Endpoints

The secondary efficacy endpoints include the following:

- **EU and RoW:** Proportion of positive pruritus assessments at the patient level over the 72-week treatment period using the Albireo ObsRO instrument.
- **US:** Change from baseline in fasting serum bile acids after 72 weeks of treatment.
- **All Regions:**

- Change from baseline in serum bile acids at Weeks 4, 12, 22, 24, 36, 46, 48, 60, 70, 72, 76 and all visits (every 16 weeks) during the optional extension period.
- Proportion of individual assessments meeting the definition of a positive pruritus assessment at the patient level using the Albireo ObsRO instrument from Weeks 0-4, Weeks 0-12, Weeks 0-22, Weeks 0-24, Weeks 0-36, Weeks 0-46, Weeks 0-48, Weeks 0-60, and Weeks 0-70, and the proportion of positive pruritus assessments at each 4--week interval between Visit 1/Screening and Visit 5/Week 24, then by each visit between Visit 5/Week 24 and Visit 12/Week 76.
- Proportion of individual AM assessments meeting the definition of a positive pruritus assessment at the patient level using the Albireo ObsRO instrument from Weeks 0-4, Weeks 0-12, Weeks 0-22, Weeks 0-24, Weeks 0-36, Weeks 0-46, Weeks 0-48, Weeks 0-60, Weeks 0-70, and Weeks 0-72, and the proportion of positive pruritus assessments at each 4-week interval between Visit 1/Screening and Visit 5/Week 24, then by each visit between Visit 5/Week 24 and Visit 12/Week 76.
- Proportion of individual PM assessments meeting the definition of a positive pruritus assessment at the patient level using the Albireo ObsRO instrument from Weeks 0-4, Weeks 0-12, Weeks 0-22, Weeks 0-24, Weeks 0-36, Weeks 0-46, Weeks 0-48, Weeks 0-60, Weeks 0-70, and Weeks 0-72, and the proportion of positive pruritus assessments at each 4-week interval between Visit 1/Screening and Visit 5/Week 24, then by each visit between Visit 5/Week 24 and Visit 12/Week 76.
- Number of patients undergoing biliary diversion surgery or liver transplantation. These parameters will be evaluated separately and together at Weeks 24, 48, 72 and all visits (every 16 weeks) during the optional extension period.
- Change in growth from baseline to Weeks 12, 24, 36, 48, 60, 72 and all visits (every 16 weeks) during the optional extension period after initiation of odevixibat treatment, defined as the linear growth deficit (height/length

for age, weight for age, and BMI) compared to a standard growth curve (Z-score, StdDev from the fiftieth percentile, P50).

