8.1 Handling of Missing Data and/or Invalid Data and Outliers

8.1.1 Missing Data Analysis Methods for Efficacy Endpoints

No imputation will be made for any missing data. The assessments after intercurrent events (death, or initiation of rescue treatments such as biliary diversion surgery or liver transplantation) or follow-up assessments (\geq last dose day + 15 days) will be excluded from analysis with the exception of the analysis of patients undergoing biliary diversion surgery or liver transplantation. For eDiary data analysis, data after last dose will be excluded from analysis.

9. Statistical Methods

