9.6 Efficacy Analyses

This section addresses the analyses to be conducted on the primary, secondary, and exploratory efficacy variables.

The efficacy analysis will be carried out using the patients from the FAS. Figures for selected efficacy endpoints, such as the primary pruritus endpoint, change in serum bile acids, and change in other patient-reported and caregiver-reported outcomes, will be provided by cohort/treatment subgroup and by visit. Forest plots will be provided for the efficacy subgroup analyses.

For efficacy endpoints derived from central laboratory data, if central laboratory data are not available due to COVID-19 or other reasons, local laboratory data will be used and converted to standard unit used by central laboratory. In addition, laboratory related efficacy endpoints will only be considered up to 14 days follow-up after the last dose.

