9.7 Safety Analyses

All definitions relative to safety endpoints are detailed in [Section 4.4](#).

All the safety analyses will be performed on the FAS for all safety variables specified below and summarised by cohort/treatment subgroup and overall.

For each safety variable, the last value collected before the first dose of study drug will be used as baseline (i.e., Baseline 2 defined in the table of derived variables in [Appendix A](#)) for all analyses unless otherwise specified.

In addition, different with efficacy analysis, laboratory related safety endpoints will be considered up to 28 days follow-up after the last dose.

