Appendix B: Visit Window

The observation closest to the target day is the measurement used in the analysis for each visit. The following visit window will apply for all laboratory parameters, questionnaires, vital signs, physical measurements and other efficacy parameters in the study, if not otherwise specified.

Table 4: Analysis Visit Window (General)

TIMING OF ASSESSMENT (DAYS RELATIVE TO TREATMENT)	VISIT NAME TO DISPLAY FOR ANALYSIS	TARGET DAY	STUDY DAY (RELATIVE DAY)
Screening (Days -56 to -1)	Baseline		≤ -1
Day 1 Week 1	Baseline		1 (Pre-dose)
Week 4 (± 5 days)	Week 4	28	Post-baseline - 56
Week 12 (± 7 days)	Week 12	84	57–119
Week 22 (± 7 days)	Week 22	154	120–161
Week 24 (± 7 days)	Week 24	168	162–210
Week 36 (± 7 days)	Week 36	252	211–287
Week 46 (± 7 days)	Week 46	322	288–329
Week 48 (± 7 days)	Week 48	336	330–378
Week 60 (± 7 days)	Week 60	420	379–455
Week 70 (± 7 days)	Week 70	490	456–497
Week 72/EOT (± 7 days)	Week 72	504	498–(Last dose day + 14)
4 weeks post last dose of study drug (± 7 days)	Follow-up	28 post last dose	Last dose day + 15–Last dose day + 28
For patients who enter optional extension period:			
Week 72/EOT (± 7 days)	Week 72	504	498– Min(518, start day of optional extension period -1)
Week 88	Week 88	616	Min(519, start day of optional extension period)–672
Week 104, 120, ... (continue every 16 weeks)	Week 104, 120, ... (continue every 16 weeks)	7*week #	(7*(week # - 8) + 1) – Min(7*(week # + 8), Last dose day + 14)

Table 5: Analysis Visit Windows for GIC/GIS, Physical Measurements and Selected Lab Test)

TIMING OF ASSESSMENT (DAYS RELATIVE TO TREATMENT)	VISIT NAME TO DISPLAY FOR ANALYSIS	TARGET DAY	STUDY DAY (RELATIVE DAY)
Screening (Days -56 to -1)	Baseline		≤ -1
Day 1 Week 1	Baseline		1 (Pre-dose)
Week 4 (± 5 days)	Week 4	28	Post-baseline - 56
Week 12 (± 7 days)	Week 12	84	57–126
Week 24 (± 7 days)	Week 24	168	127–252
Week 48 (± 7 days)	Week 48	336	253–420
Week 72/EOT (± 7 days)	Week 72	504	421–(Last dose day + 14)
4 weeks post last dose of study drug (± 7 days)	Follow-up	28 post last dose	Last dose day + 15–Last dose day + 28
For patients who enter optional extension period:			
Week 72/EOT (± 7 days)	Week 72	504	421– Min(518, start day of optional extension period -1)
Week 88	Week 88	616	Min(519, start day of optional extension period)–672
Week 104, 120, ... (continue every 16 weeks)	Week 104, 120, ... (continue every 16 weeks)	7*week #	(7*(week # - 8) + 1) – Min(7*(week # + 8), Last dose day + 14)

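### The Follow-up analysis window stops on its own target day despite a ±7-day visit tolerance, and the Week 76 efficacy summaries are emptied by the plan's own cut-offs

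*SAP*

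**What the plan says.** **Follow-up window.** The Follow-up row is the same in Tables 4, 5 and 6 of Appendix B. The timing is given as "4 weeks post last dose of study drug (± 7 days"), the target day as "28 post last dose", and the analysis window as "Last dose day + 15–Last dose day + 28". Section 9.7 adds that "laboratory related safety endpoints will be considered up to 28 days follow-up after the last dose". Section 3.1 times the visit in two ways. For patients not entering the extension, "Visit 12 was to take place 28 days after Visit 11"; for patients withdrawn early it falls 28 days after the last dose.

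**Week 76 efficacy.** Section 4.2 lists "Change from baseline in serum bile acids at Weeks 4, 12, 22, 24, 36, 46, 48, 60, 70, 72, 76" and takes the by-visit pruritus proportions up to Visit 12/Week 76. Sections 4.3, 9.6.4 and 9.6.5 do likewise for pruritus, itching/scratching and sleep summaries. Table 7 has a Weeks 72–76 row starting at Day 505 with 28 expected diary days. Sections 3.3.1 and 3.3.2 have bile acids drawn through Visit 12 and the diary kept without a break from Visit 11 to Visit 12.

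Against this, Section 8.1.1 drops efficacy assessments from last dose +15 onward and states: "For eDiary data analysis, data after last dose will be excluded from analysis". Section 9.6 states that "laboratory related efficacy endpoints will only be considered up to 14 days follow-up after the last dose". The only exception in Section 8.1.1 is the analysis of biliary diversion and transplantation.

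**The concern.** A window that ends on its target day covers visits that are early or exactly on time, but none that are late within tolerance. A patient who attends two days late, as the plan allows, contributes nothing to the Follow-up column. Because of the 28-day limit in Section 9.7, that patient's results also cannot enter the change-to-last-visit summary or the highest/lowest post-baseline shift tables of Section 9.7.2. An abnormal liver test on day +30 from a compliant visit would appear only in a listing.

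The efficacy problem is a contradiction: the plan both requires and forbids the same secondary and exploratory summaries. Whoever programs the tables must either produce empty Week 76 rows or set the cut-offs aside, and would make that choice with the data in hand.

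**Working it through.** LD denotes the day of last dose. The check is day counting on figures in the SAP.

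**1. Follow-up window**

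- Permitted visit days: 28 − 7 = 21 to 28 + 7 = 35, so LD+21 to LD+35. Count: 35 − 21 + 1 = 15.
- Inside the window LD+15 to LD+28: LD+21 to LD+28. Count: 28 − 21 + 1 = 8.
- In no window: LD+29 to LD+35. Count: 35 − 29 + 1 = 7, and 7/15 = 47% of permitted days.

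Sensitivity to the Section 3.1 timing: suppose a completer's last dose is the day before Visit 11 and ±7 days applies around Visit 11 + 28. The SAP does not state this; the dose-after-visit rule in Section 3.3 names Visits 1 to 10 and the extension visits. Then an exactly on-time Visit 12 is LD+29, already outside. Permitted days are LD+22 to LD+36; 7 are inside and 8 of 15 (53%) outside.

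Comparison with the other scheduled rows of Table 4: each on-treatment window through Week 72 reaches at least its target plus tolerance (for example Week 22: 154 + 7 = 161, window to 161; Week 70: 490 + 7 = 497, window to 497). Weeks 24, 48 and 72 start one day inside their lower tolerance (162 against 161, 330 against 329, 498 against 497), but that day belongs to the preceding window. Among these rows, Follow-up is the only one in which a compliant visit has no window at all.

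**2. Week 76 serum bile acids**

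- Efficacy laboratory data are eligible up to LD+14.
- The earliest permitted follow-up day is LD+21, so 0 of 15 permitted days are eligible.
- The Follow-up window itself begins at LD+15, the day after the cut-off, so the two do not overlap.

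**3. Weeks 72–76 diary interval (Day 505 onward)**

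- Eligible days = last-dose day − 504, because diary data after the last dose are excluded.
- Required under the 50% rule: 0.5 × 28 = 14 days.

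| Last dose on study day | Eligible diary days | Meets 14? |
|---|---|---|
| 504 (Week 72 on target) | 0 | No |
| 511 (504 + 7, latest within tolerance) | 7 | No |
| 518 | 14 | Yes |

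Only a patient still dosed on Day 518 or later could fill the row, and those would be on-treatment days under a follow-up label. Patients in the extension stop the diary at Visit 11 (Section 3.3.2), so they cannot fill it either.

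**The case against.** The strongest reply is that the limits are deliberate. Section 10 declares both the 28-day TEAE period and the 14-day efficacy laboratory limit as changes from the protocol, and Sections 9.7 and 9.7.1 use 28 days consistently. A 28-day safety horizon and an on-treatment efficacy estimate are legitimate choices. That stands, and it means deleting Week 76 is as valid a reconciliation as analysing it. It does not explain why the visit may take place a week beyond the window, or why the Week 76 endpoints remain.

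Several stronger readings might be inferred, and the SAP does not support them:

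- *Half of the follow-up results are lost.* The 47% is a share of permitted days. No visit dates are given and visits may cluster at the target. For early withdrawals the visit is timed from the last dose, so an on-time visit is inside the window.
- *The data are discarded.* Laboratory results and all AEs, including post-treatment ones, are listed (Sections 9.7.1 and 9.7.2). The loss is from summaries.
- *These are the only check on late hepatic change.* TEAEs run to 28 days, and the DSMB adjudicates hepatic events on criteria that cite no visit window. The SAP text also does not say which safety tests are drawn at Visit 12 and leaves the schedule to the protocol; it names only bile acids as drawn through that visit.
- *Week 76 is the only off-drug comparison.* Baseline 2 precedes odevixibat for Cohort 2 and for patients who had placebo in Study A4250-005, and Baseline 1 does so for the rest of Cohort 1. Week 76 is at most a withdrawal contrast.

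One caution on the remedy also stands: a 35-day laboratory limit beside a 28-day TEAE period allows an abnormal value into a table while an AE starting on the same day is not treatment-emergent.

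**Conclusion.** Both points hold as inconsistencies in the plan and should be corrected; neither threatens the main conclusions. Seven of 15 permitted follow-up days fall in no window, or 8 of 15 if the last dose precedes Visit 11 by a day. The number of patients this removes from the summaries is unknown. The Week 76 bile acid summary is empty by rule, and the Weeks 72–76 diary row is empty for anyone whose last dose is within the Week 72 tolerance.

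The effect is confined to patients who have a Follow-up visit; those continuing into the extension at Week 72 do not have one then. The primary endpoints, which use Weeks 70 and 72 for bile acids and Weeks 0–72 for pruritus, are not affected. The result rests on reading the ±7 days in the Follow-up row as the visit tolerance around the stated target.

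**What to change.** 1. Set the Follow-up window to last dose +15 to last dose +35 in Table 4, and in Tables 5 and 6 for any assessment actually done at Visit 12. Align the Section 9.7 laboratory limit to +35, and add a note that the TEAE period remains 28 days. This covers 15 of 15 permitted days instead of 8, or 14 of 15 instead of 7 under the day-before assumption. The downside is that a few values from beyond 28 days enter the safety tables, with the mismatch to the TEAE period that the note should explain.

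2. For Week 76, choose one and state it. Either exempt the Week 76 bile acids and the Weeks 72–76 diary interval from the cut-offs in Sections 8.1.1 and 9.6, and report them descriptively as off-treatment follow-up, kept out of every on-treatment estimate. Or delete Week 76 from the endpoints and analyses in Sections 4.2, 4.3, 9.6.4 and 9.6.5, together with the Day 505 row of Table 7.

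The cost is a few table cells and sentences. No additional data collection is needed, and the on-treatment estimates do not change.

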Weeks 44 – 46	288 – 322	Weeks 42 – 46 (21 days)
Weeks 47 – 48	323 – 378	Weeks 47 – 54 (14 days)
Weeks 58 – 60	379 – 455	Weeks 55 – 65 (21 days)
Weeks 68 – 70	456 – 490	Weeks 66 – 70 (21 days)
Weeks 71 – 72	491 – 504	Weeks 71 – 72 (14 days)
Weeks 72 – 76	>=505	>=505 (28 days)

^a The proportion of positive pruritus assessments is calculated based on reported data only. The assessments after intercurrent events (premature treatment discontinuation, death, or initiation of rescue treatments such as biliary diversion surgery or liver transplantation) will be excluded from the calculation.

^b To have an appropriate analysis, only include patients who reported at least 50% of expected data during the interval. Of notes, for Weeks 34 – 36, while eDiary data during weeks 25 to 41 will be included for analysis, 50% rule is applied to Weeks 31 – 41 only to make sure that a patient is on treatment long enough for the analysis of Weeks 34 – 36.

Table 8: Analysis Visit Window for Proportion of Responders for Pruritus Monthly Scores

4-WEEK/BY-VISIT INTERVAL	INTERVALS TO INCLUDE EDIARY DATA (DAYS) ^a	INTERVALS WITH >=50% OF EXPECTED DATA TO INCLUDE PATIENTS ^b (# OF EXPECTED DAYS TO REPORT EDIARY)
Weeks 1 – 4	1 – 28	Weeks 1 – 4 (28 days)
Weeks 5 – 8	29 – 56	Weeks 5 – 8 (28 days)
Weeks 9 – 12	57 – 84	Weeks 9 – 12 (28 days)
Weeks 13 – 16	85 – 112	Weeks 13 – 16 (28 days)
Weeks 17 – 20	113 – 140	Weeks 17 – 20 (28 days)
Weeks 21 – 24	141 – 168	Weeks 21 – 24 (28 days)
Weeks 34 – 36	169 – 287	Weeks 31 – 41 (21 days)
Weeks 45 – 48	288 – 378	Weeks 42 – 54 (28 days)
Weeks 58 – 60	379 – 455	Weeks 55 – 65 (21 days)
Weeks 68 – 72	456 – 504	Weeks 66 – 72 (28 days)

^a The proportion of responders for pruritus monthly scores is calculated based on reported data only. The assessments after intercurrent events (premature treatment discontinuation, death, or initiation of rescue treatments such as biliary diversion surgery or liver transplantation) will be excluded from the calculation.

^b To have an appropriate analysis, only include patients who reported at least 50% of expected data during the interval. Of notes, for Weeks 34 – 36, while eDiary data during weeks 25 to 41 will be included for analysis, 50% rule is applied to Weeks 31 – 41 only to make sure that a patient is on treatment long enough for the analysis of Weeks 34 – 36.

Table 9: Analysis Visit Window for Proportion of Responders for Pruritus Bi-weekly Scores

BI-WEEKLY/BY-VISIT INTERVAL	INTERVALS TO INCLUDE EDIARY DATA (DAYS) ^a	INTERVALS WITH >=50% OF EXPECTED DATA TO INCLUDE PATIENTS ^b (# OF EXPECTED DAYS TO REPORT EDIARY)
Weeks 1 – 2	1 – 14	Weeks 1 – 2 (14 days)
Weeks 3 – 4	15 – 28	Weeks 3 – 4 (14 days)
Weeks 5 – 6	29 – 42	Weeks 5 – 6 (14 days)
Weeks 7 – 8	43 – 56	Weeks 7 – 8 (14 days)
Weeks 9 – 10	57 – 70	Weeks 9 – 10 (14 days)
Weeks 11 – 12	71 – 84	Weeks 11 – 12 (14 days)
Weeks 13 – 14	85 – 98	Weeks 13 – 14 (14 days)
Weeks 15 – 16	99 – 112	Weeks 15 – 16 (14 days)
Weeks 17 – 18	113 – 126	Weeks 17 – 18 (14 days)
Weeks 19 – 20	127 – 140	Weeks 19 – 20 (14 days)
Weeks 21 – 22	141 – 154	Weeks 21 – 22 (14 days)
Weeks 23 – 24	155 – 168	Weeks 23 – 24 (14 days)
Weeks 35 – 36	239 – 252	Weeks 35 – 36 (14 days)
Weeks 47 – 48	323 – 336	Weeks 47 – 48 (14 days)
Weeks 59 – 60	407 – 420	Weeks 59 – 60 (14 days)
Weeks 71 – 72	491 – 504	Weeks 71 – 72 (14 days)

^a The proportion of responders for pruritus bi-weekly scores is calculated based on reported data only. The assessments after intercurrent events (premature treatment discontinuation, death, or initiation of rescue treatments such as biliary diversion surgery or liver transplantation) will be excluded from the calculation.

^b To have an appropriate analysis, only include patients who reported at least 50% of expected data during the interval. Of notes, for Weeks 35 – 36, while eDiary data during weeks 35 to 36 will be included for analysis, 50% rule is applied to Weeks 35 – 46 only to make sure that a patient is on treatment long enough for the analysis of Weeks 35 – 36.

Table 10: Analysis Visit Window for Proportion of Positive Pruritus Assessment

CUMULATIVE INTERVAL	INTERVALS TO INCLUDE EDIARY DATA (DAYS) ^a (# OF EXPECTED DAYS TO REPORT EDIARY)	INTERVALS WITH >=50% OF EXPECTED DATA TO INCLUDE PATIENTS ^b (# OF EXPECTED DAYS TO REPORT EDIARY)
Weeks 0 – 4	1 – 28 (28 days)	Weeks 1 – 4 (28 days)
Weeks 0 – 12	1 – 84 (84 days)	Weeks 9 – 12 (28 days)
Weeks 0 – 22	1 – 154 (154 days)	Weeks 19 – 22 (28 days)
Weeks 0 – 24	1 – 168 (168 days)	Weeks 21 – 24 (28 days)
Weeks 0 – 36	1 – 287 (189 days)	Weeks 31 – 41 (21 days)
Weeks 0 – 46	1 – 322 (210 days)	Weeks 42 – 46 (21 days)
Weeks 0 – 48	1 – 378 (224 days)	Weeks 47 – 54 (14 days)
Weeks 0 – 60	1 – 455 (245 days)	Weeks 55 – 65 (21 days)
Weeks 0 – 70	1 – 490 (266 days)	Weeks 66 – 70 (21 days)
Weeks 0 – 72	1 – 504 (280 days)	Weeks 71 – 72 (14 days)

^a The proportion of positive pruritus assessments is calculated based on reported data only when >=50% of expected ediary data is reported. The assessments after intercurrent events (premature treatment discontinuation, death, or initiation of rescue treatments such as biliary diversion surgery or liver transplantation) will be excluded from the calculation.

^b To have an appropriate analysis, only include patients who reported at least 50% of expected data during the interval. Of notes, for Weeks 0 – 36, while eDiary data during weeks 0 to 41 will be included for analysis, 50% rule is applied to Weeks 31 – 41 only to make sure than a patient is on treatment long enough for the analysis of Weeks 0 – 36.

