9.6.3 Analyses of Primary Efficacy Endpoints

All the primary analyses will be based on the FAS, unless otherwise specified.

For the EU and RoW, change from baseline 2 in fasting serum bile acids will be analysed by using the 1-sample t-test or the Wilcoxon signed rank test, as appropriate at the end of the 72-week treatment period based on the average of the values at Weeks 70 and 72. Baseline 2, defined in the table of derived variables in [Appendix A](#), will be used to calculate change from baseline for the summary.

For Cohort 1 patients who were on odevixibat in Study A4250-005, change from Baseline 1 to end of the 72-week treatment in Study A4250-008 will be analysed by using the 1-sample t-test or the Wilcoxon signed rank test, as appropriate. Baseline 1,

defined in the table of derived variables in [Appendix A](#), will be used for this statistical analysis.

For the US, the proportion of positive pruritus assessments at the patient level over the 72-week treatment period using the Albireo ObsRO instrument will be summarised descriptively. A positive pruritus assessment is defined as a scratching score of ≤ 1 or at least a 1-point drop from baseline on the Albireo ObsRO instrument. At each assessment, the AM score will be compared to the baseline AM average, and the PM score will be compared to the baseline PM average. Both AM and PM pruritus assessments will be included in the analysis of this endpoint. For analysis purposes, diary entries will be assigned to a study day based on the recorded date regardless of recorded time. AM scores from the period of 14 days before or on the first dose day in Study A4250-008 will be averaged as AM baseline. PM scores from the period of 14 days before the first dose day in Study A4250-008 will be averaged as PM baseline. If a patient's baseline score is ≤ 1 , then only the criterion of a one-point drop from baseline on the Albireo ObsRO instrument will be used to determine whether a pruritus assessment is positive or not for the primary endpoint analysis. Rounded baseline score will be used for the analysis.

A 95% CI will be provided for the proportion of positive pruritus assessments.

Change from Baseline 1 and 2 in monthly scratching severity score to end of the 72-week treatment in Study A4250-008 will be analysed by using the 1-sample t-test or the Wilcoxon signed rank test, as appropriate. Baseline 1 will only be used for patients in Cohort 1 who were on odevixibat in Study A4250-005.

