AM & PM baseline, daily, weekly, and monthly score (scratching, itch severity)	
For both the Albireo ObsRO scratching item and the Albireo PRO itch severity score:
 
A daily AM & PM score will be averaged from the 2 ratings for each day. A daily score will be considered missing if both assessments are missing.
 
A weekly score will be calculated by averaging all non-missing AM and PM scores in a week. A weekly score will be considered missing if ≥ 8 out of 14 assessments in a week are missing.
 
A monthly score will be calculated by averaging all non-missing AM and PM scores in a month (28 days). A monthly score will be considered missing if ≥ 29 out of 56 assessments in a month are missing.
 
An average score of AM & PM at each visit after Week 24 will be calculated by averaging all non-missing AM and PM scores between 2 visits with analysis windows applied (Appendix B). 50% rule is applied based on the number of planned assessments.
 
All non-missing AM scores from the period of 14 days before or on the first dose day of study medications, and all non-missing PM scores from the period of 14 days before the first dose day of study medications will be averaged as the AM & PM baseline score. Baseline score will be considered missing if ≥ 15 out of 28 assessments in the 14 days are missing. Rounded baseline score will be used for the analysis.
 
One thing of note:
 
Inclusion criteria No. 4 in Study A4250-005:
 
Cohort 1: Patient must have history of significant pruritus and a caregiver-reported observed scratching in the eDiary average of ≥ 2 (on 0 to 4 scale) in the 2 weeks prior to randomisation in Study A4250-005.
 
Inclusion criteria No. 4 in Study A4250-008:
 
Cohort 2: Patient must have history of significant pruritus and a caregiver-reported observed scratching or patient reported itching (for patients > 18 with no caregiver-reported observed scratching) in the eDiary average of ≥ 2 (on 0 to 4 scale) in the 2 weeks prior to the screening/inclusion visit (Visit 1) in Study A4250-008.
 
The pruritus score for purposes of establishing eligibility was calculated by taking the average of the worse of the two scores for each day. The values for week one were averaged and the values for week 2 were averaged. The two weekly averages were then averaged to provide a single score. If this score was ≥ 2 the pruritus eligibility requirement was met. The calculation of pruritus eligibility score is different from the calculation of the baseline pruritus score defined in the SAP.

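### Table 8 counts 28 expected diary days for the Week 48 and Week 72 monthly responder scores where Tables 7 and 10 and the diary schedule give 35, so 40% completeness passes a 50% rule

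*SAP*

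**What the plan says.** Appendix B of the SAP holds several diary window tables. Each gives the study days whose entries are used, and a second interval, with a count of expected diary days, on which a 50% completeness requirement is applied.

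- Table 8 (monthly responder scores), Week 72 row, data from days 456 to 504: "Weeks 66 – 72 (28 days".
- Table 8, Week 48 row, data from days 288 to 378: "Weeks 42 – 54 (28 days".
- Table 7 (by-visit diary parameters) splits the first of these blocks into days 456 to 490, "Weeks 66 – 70 (21 days", and days 491 to 504, "Weeks 71 – 72 (14 days".
- Table 7 splits the second into days 288 to 322, "Weeks 42 – 46 (21 days", and days 323 to 378, "Weeks 47 – 54 (14 days".
- Table 10 (cumulative proportion of positive assessments) gives running totals of 189, 224, 245 and 280 expected days to days 287, 378, 455 and 504.

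Footnote b to Table 8 restricts each interval to patients with half or more of the expected data.

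Section 9.6.3 also plans a one-sample t-test or Wilcoxon signed rank test of "Change from Baseline 1 and 2 in monthly scratching severity score to end of the 72-week treatment in Study A4250-008". It names no window. Appendix A obtains a monthly score by "averaging all non-missing AM and PM scores in a month (28 days" and treats it as missing when 29 or more of 56 assessments are missing. For visits after Week 24, Appendix A separately describes a between-visit average that uses the Appendix B windows, with the 50% rule based on planned assessments.

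**The concern.** Three tables in one appendix cover the same study days under one diary schedule, so their expected counts should agree. In two rows of Table 8 they do not. The expected count is the denominator of the completeness rule, so understating it lowers the bar for evaluability below the level the SAP sets. The Week 48 and Week 72 monthly responder proportions would then include patients whose late diaries are sparser than the plan allows.

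A second, smaller matter is that Section 9.6.3 tests a monthly score at the end of 72 weeks, while Appendix A's 28-day month and Table 8's days 456 to 504 are different spans. The row that applies should be fixed before the data are analysed.

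**Working it through.** **Inputs.** Sections 3.1 and 3.3.2 call for diary entries twice daily to Week 24 and then for the 21 days before each clinic visit. After Week 24 and up to Week 72, the clinic visits fall at Weeks 36, 46, 48, 60, 70 and 72. Visits are taken on their nominal days (7 × week number).

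**Count from the schedule, with overlapping days counted once.**

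- Week 48 block: days 302–322 before Week 46 and days 316–336 before Week 48. They overlap on days 316–322 (7 days). 21 + 21 − 7 = 35, namely days 302–336.
- Week 72 block: days 470–490 before Week 70 and days 484–504 before Week 72. They overlap on days 484–490 (7 days). 21 + 21 − 7 = 35, namely days 470–504.

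**Does this count reproduce the SAP's figures?** It gives all ten cumulative totals in Table 10 (28, 84, 154, 168, 189, 210, 224, 245, 266, 280), all six rows of Table 7 from Week 25 to Week 72, and eight of the ten rows of Table 8. Only these two fail:

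| Days | Table 8 | Table 7 | Table 10 | Schedule |
|---|---|---|---|---|
| 288–378 | 28 | 21 + 14 = 35 | 224 − 189 = 35 | 35 |
| 456–504 | 28 | 21 + 14 = 35 | 280 − 245 = 35 | 35 |

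The Table 8 column sums to 6 × 28 + 21 + 28 + 21 + 28 = 266, against 280 in Table 10. The gap of 14 is 7 days in each of the two rows.

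**Labels.** Weeks 68 to 72 are days 470–504, which is 35 days, so the Week 72 label already contradicts the 28 beside it. Weeks 45 to 48 are days 309–336, which is 28 days, but Table 7 starts the same block at Week 44. Weeks 44 to 48 are days 302–336, which is 35 days.

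**Effect on the rule.**

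- As written: 50% of 28 = 14 days, or 28 of 56 assessments. Against what is scheduled, 14/35 = 28/70 = 40%.
- At a true 50%: 35 of 70 assessments, or 17.5 days, so 18 when whole days are counted (18/35 = 51%).
- Admitted below the stated standard: patients with 14 to 17 complete days (14/35 = 40% to 17/35 = 49%).

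**Candidate spans for the Section 9.6.3 score.** A 28-day month ending at Week 72 is days 477–504, with 28 expected days. The Table 8 row is days 456–504: 49 calendar days with 35 expected diary days.

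**The case against.** The best defence is that 28 is a deliberate ceiling. Table 8 concerns monthly scores, Appendix A fixes a month at 28 days, and taking the smaller of 28 and the scheduled days reproduces all ten rows, including the 21s at Weeks 36 and 60. The numerical fit is real. But no such ceiling is stated, the column is headed as a count of days on which reporting is expected, and Appendix A bases the rule after Week 24 on planned assessments. Even with a ceiling, footnote b would be breached, because 14 days is still 40% of what is expected in the interval.

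Other objections stand and limit the point.

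- A reader might infer that the Week 72 scratching score has three rival definitions. The SAP does not support that. Table 7 serves the by-visit output, and the monthly responder endpoint has one stated data window, days 456–504. What remains is that Section 9.6.3 names no row.
- A reader might also infer that the tested score is itself compromised. That is conditional: Table 8 is titled for responders only, and whether it governs the test is exactly what is unstated.
- It is tempting to blame the 28 for patients who count at Week 72 without any entries in Weeks 71 and 72. The wide window causes that. Someone with entries on days 470–487 (18 days) has none in Weeks 71 and 72 and still passes with 35 as the denominator.
- Narrowing the window to the last 28 days would redesign windows that the SAP makes wide on purpose after Week 24, and Table 8 has no row labelled Weeks 69 to 72.

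**Conclusion.** The inconsistency is established. Two cells of Table 8 say 28 where Table 7, Table 10 and the diary schedule say 35, and the working threshold at Weeks 48 and 72 is 40% of expected data instead of 50%. The counts assume nominal visit days, which also reproduce Tables 7 and 10.

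The scope is limited. The descriptive secondary responder endpoint, in its monthly form, is affected at two time points. The bi-weekly version uses Table 9, whose 14-day counts match its 14-day windows. The Section 9.6.3 monthly-score test is affected only if it uses Table 8. The US primary endpoint is unaffected, and Section 5 states that there is no formal hypothesis testing. The SAP gives no figure for how many patients have 14 to 17 late diary days; the number is probably small. The point is worth correcting because it decides who is evaluable, but it does not threaten the main conclusions.

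**What to change.** - In Table 8, change the expected count to 35 days in the Week 48 row (days 288–378) and the Week 72 row (days 456–504). State the requirement as at least 35 of 70 planned AM and PM assessments, which is about 18 days; 17 full days plus one further entry would also meet it.
- Relabel the row for Weeks 45 to 48 as Weeks 44 to 48, to match Table 7 and the 35 days.
- Add a sentence to Section 9.6.3 naming the Appendix B row that defines the end-of-Week-72 monthly scratching score, so that the choice between Appendix A's 28-day month and days 456–504 is made in advance.

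The data windows stay as they are. The cost is two counts, one label and one sentence, and patients with only 14 to 17 late diary days become non-evaluable in those two rows. If the database is already locked, the correction should be reported in the clinical study report as a deviation from the SAP, as Section 1 provides.
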